9.2 Description of visits

9.2.1 Visit 1 (screening /randomization and intravenous therapy, Days 1-3(7) of the study)

The Visit 1 is scheduled on Days 1-3(7) of the study and will be performed at hospital. On Day 1 (no more than 24 hours) all screening procedures should be performed and eligible patients should be randomized and after randomization will receive the first intravenous dose of IMP. On Days 2-3(7) patients will receive intravenous therapy.

Therefore during the Visit 1 the following procedures will be performed:

Screening procedures (Day 1)

To evaluate the selection criteria of the study, the Investigator may use laboratory test results obtained at the laboratory of the investigational site within 24 hours of study enrollment (Signing of the Informed Consent Form) if he / she considers that available data are sufficient to permit a decision on whether the subject meets the selection criteria. In this case, another blood sampling procedure has to be conducted in the period from the signing of the Informed Consent Form to the start of treatment in order to evaluate all other laboratory parameters that have to be determined on Day 1 in accordance with the study protocol

- Obtainment of written informed consent (before all other procedures)
- Demographic and other baseline characteristic data collection
- Medical history taking
- Pregnancy test (for women of childbearing potential only)
- Physical examination
- Assessment of vital signs
- ECG (before or 30 minutes after blood samples collection)
- Haematology test
- Biochemical assay
- Urinalysis
- Documentation of SAEs occurred after the obtainment of the informed consent (after the signing of ICF)
- Chest x-ray (two-dimensional roentgenogram) or computed tomography. The results of chest x-ray (computed tomography) performed within 72 hours before enrollment are acceptable
- Pulse oximetry
- Collection of sputum sample for culture (if the patient has sputum)
- Collection of blood sample for culture
- Assessment of prior medication taken within 30 days before the Visit and therapies (beginning from the onset of community-acquired pneumonia)
- Check of inclusion/exclusion criteria

CONFIDENTIAL Page 48 of 88

Randomization and initiation of therapy (Day 1)

- Before starting the therapy patients eligible for inclusion will be randomized
- Start of intravenous therapy with IMP
- Assessment of vital signs 2 hours ± 30 minutes after the second infusion (Tavanic®/Placebo) is finished
- Documentation of AEs/SAEs occurred after the first IMP administration
- Compliance check
- Assessment of concomitant medication and therapies
- Blood sample collection for PK (via venous catheter): pre-dose, 0 h, 0.5 h (±3min), 2.5h (±5min), 4h (±5min), 6h (±10min), 12h (±15min), 16h (±15min) and 22.5h (±15min) after the end of first infusion (**only for investigational sites defined by the Sponsor**). The last blood sampling for PK (22.5h after the end of the first infusion) should be conducted prior to the IMP infusion on Day 2.

Continuation of intravenous therapy (Days 2-3(7))

All of the following procedures should be performed on each day of Days 2-3(7) of the study:

- Physical examination before dosing
- Assessment of vital signs before dosing
- Intravenous therapy with IMP
- Assessment of vital signs 2 hours ± 30 minutes after the second infusion is finished
- Documentation of AEs/SAEs
- Compliance check
- Assessment of concomitant medication and therapies

9.2.2 Visit 2 (switch to oral therapy/oral therapy, Days 4(8)-7(14) of the study)

Visit 2 is scheduled on Days 4(8)-7(14) of the study and will be performed at hospital.

On Day 4(8) of the study the investigator will assess patient's medical condition and if the patent meets specified criteria he/she (see APPENDIX 2: ASSESSMENT OF CLINICAL STABILITY (POSSIBILITY OF SWITCH TO ORAL TREATMENT)) could be switched to oral treatment. However if the treatment with intravenous IMP should be prolonged after the 7 days of treatment are completed, according to the investigator's opinion, the investigator should contact the study Medical Adviser (see Contact information) for the approval of intravenous treatment prolongation. Despite prolonged intravenous therapy, the overall duration of treatment within this study will not exceed 14 days.

Note that the first dose of oral drug will be administered on the day when the switch is performed (e.g. the patient will receive the first dose of oral drug on Day 4 if the switch is performed at Day 4, etc.). Therefore, oral treatment will be started since Day 4(8) of Visit 2 and will last until and including Day 7(14) of Visit 2.

CONFIDENTIAL Page 49 of 88

Switch to oral therapy (Day 4(8))

All the procedures scheduled on Day 4(8) of Visit 2 should be performed within one day. The following measures will be performed during Day 4(8) of the Visit 2 in accordance with the study schedule of assessments:

- Physical examination (before dosing)
- Assessment of vital signs (before dosing)
- ECG (before dosing; before or 30 minutes after blood samples collection)
- Haematology test (before dosing)
- Biochemical assay (before dosing)
- Urinalysis (before dosing)
- Pulse oximetry (before dosing)
- Collection of a sputum sample for culture (before dosing and if the patient has sputum)
- Collection of a blood sample for culture (before dosing, sampling should not be conducted in case of negative culture at Visit 1)
- Clinical response assessment
- Switch to oral therapy, the first dose of oral IMP
- Assessment of vital signs 2 hours \pm 30 minutes after oral dose administration
- Documentation of AEs/SAEs
- Compliance check
- Assessment of concomitant medication and therapies.

Continuation of oral therapy (Days 5(9)-7(14))

All of the following procedures should be performed on each day of Days 5(9)-7(14) of the study:

- Physical examination before dosing
- Assessment of vital signs before dosing
- Oral therapy with IMP
- Assessment of vital signs 2 hours \pm 30 minutes after oral dose administration
- Documentation of adverse events
- Compliance check
- Assessment of concomitant medication and therapies.

9.2.3 Visit 3 (end of treatment visit, within 1-2 days after the last dose)

Visit 3 will be performed within 1-2 days after the last dose, but not less than 24 hours after the last dose of the study drug. The Visit can be performed at outpatient department. The following measures will be performed during the Visit 3 in accordance with the study schedule of assessments:

- Physical examination
- Assessment of vital signs
- ECG (before or 30 minutes after blood samples collection)
- Haematology test

CONFIDENTIAL Page 50 of 88

- Biochemical assay
- Urinalysis
- Pulse oximetry
- Collection of a sputum sample for culture (if the patient has sputum)
- Collection of a blood sample for culture (sampling should not be conducted in case of negative culture at Visit 1)
- Clinical response assessment
- Documentation of AEs/SAEs
- Assessment of concomitant medication and therapies

All the procedures should be performed within one day.

9.2.4 Visit 4 (test of cure visit, within 7-9 days after the last dose)

Visit 4 will be performed within 7-9 days after the last dose. The Visit can be performed at outpatient department. The following measures will be performed during the visit in accordance with the study schedule of assessments:

- Physical examination
- Assessment of vital signs
- ECG (before or 30 minutes after blood samples collection)
- Haematology test
- Biochemical assay
- Urinalysis
- Chest X ray (two-dimensional roentgenogram) or chest computed tomography
- Pulse oximetry
- Collection of a sputum sample for culture (if the patient has sputum)
- Collection of a blood sample for culture (sampling should not be conducted in case of negative culture at Visit 1)
- Clinical response assessment
- Documentation of AEs/SAEs occurred since the last visit
- Assessment of concomitant medication and therapies (since the last visit)

All the procedures should be performed within one day.

9.2.5 Visit 5 (long-term follow-up visit, within 21-23 days after the last dose)

Visit 5 will be performed within 21-23 days after the last dose as a telephone contact. The date of Visit 5 is the date of per protocol study termination for the patient.

The following measures will be performed during the visit in accordance with the study schedule of assessments:

- Documentation of AEs/SAEs occurred since the last visit
- Assessment of concomitant medication and therapies (since the last visit)
- Infection relapse assessment.

All the procedures should be performed within one day.

9.3 Unscheduled Visits

Patients may visit the investigational site for an unscheduled visit at any time if they have adverse events or in case if they need medical intervention.

CONFIDENTIAL Page 51 of 88

An investigator should record the data in the source medical documents and in the eCRF. It is obligatory for an investigator to write down the following information: date of the visit, reason, the results of examinations and additional measures which were carried out during the visit.

The next visit after the unscheduled visit is carried out according to the earlier scheduled visit date in conformity with the protocol.

If the Investigator makes a decision to withdraw a subject from the study during an unscheduled visit (a so-called "early termination visit"), the minimal number of completed procedures should correspond to that of the "End of treatment visit". For more information on discontinuation of therapy and early withdrawal of subjects from the study, see Section Ошибка! Источник ссылки не найден.

10 ASSESSMENTS

10.1 Initial assessments

10.1.1 Demographic data and other baseline characteristics

Demographic information such as date of birth, sex and race will be collected before treatment initiation on Day 1 of the study (at Visit 1, screening procedures) and then will be recorded in the eCRF.

Height and weight will be measured and alcohol use status and smoking status will be obtained and recorded in the eCRF on Day 1 of the study (at Visit 1, screening procedures) before treatment as well. Height will be used for calculation of body mass index (BMI).

10.1.2 Medical history

A medical history about all current medical conditions, any significant past conditions, operations, and therapeutic or diagnostic procedures will be obtained by the investigator or sub-investigator and recorded before treatment initiation on Day 1 of the study (at Visit 1, screening procedures).

10.1.3 Pregnancy test

Pregnancy test (urine dip-strip pregnancy test) will be performed before treatment initiation on Day 1 of the study (at Visit 1, screening procedures) only in women of childbearing potential (see definition in Section 8.8).

10.1.4 Pulse oximetry

Pulse oximetry will be done to evaluate blood oxygen saturation (SaO_2) before treatment initiation on Day 1 of the study (at Visit 1, screening procedures), before dosing on Day 4(8) of the study (at Visit 2), within 1-2 days (Visit 3) and 7-9 days (Visit 4) after the last dose.

CONFIDENTIAL Page 52 of 88

10.2 Assessment of efficacy

10.2.1 Chest X-ray / Chest Computed Tomography

X-ray examination or computed tomography (CT) will be performed before treatment initiation on Day 1 (at Visit 1, screening procedures). However, the results of X-ray examination or CT performed within 72 hours before enrollment are acceptable.

Then X-ray examination or CT will be performed within 7-9 days after the last dose (at Visit 4).

Only one radiological method (X-ray imaging only or CT imaging only for all visits) should be used for a patient throughout the study.

Chest x-ray images/CT scans will be evaluated by radiologist. Radiologist's conclusion will be fixed in the source documentation.

At Visit 4 the investigator will categorize the results to one of the following categories and will document it in the eCRF:

- 1. Cured if there is not any manifestation of pneumonia according to the chest x-ray images /chest CT scans.
- 2. Improved if the chest x-ray /chest CT results are less serious relative to the baseline results (at Visit 1 or within 72 hours before enrollment).
- 3. Unchanged if there is no change in the chest x-ray /chest CT results relative to the Visit 1 (Day 1).
- 4. Worsening if the chest x-ray /chest CT results are worsening (more serious) relative to the baseline results (at Visit 1 or within 72 hours before enrollment).

10.2.2 Clinical response assessment

The investigator will evaluate clinical response to treatment on Day 4(8) of the study (at Visit 2, switch from intravenous to oral therapy), within 1-2 days (Visit 3, end of treatment) and within 7-9 days (Visit 4, test of cure) after the last dose. Criteria for evaluation of clinical response to the therapy are presented in Table 10-1.

Table 10-1 Criteria for evaluation of clinical response

Category	Criteria
Clinical success	 All signs and symptoms of pneumonia presented at Visit 1 (Day 1) are resolved (i.g., resolution of fever, absence of intoxication, purulent sputum, and respiratory insufficiency) or improved with no worsening or appearance of new signs and symptoms of pneumonia. There is no requirement for additional antibiotic therapy. Chest roentgenograms (CT scans) are cured or improved (only for TOC visit).
Clinical failure	 Persistence or worsening in signs and symptoms of the acute process with either failure to show improvement in the clinical findings, initial improvement in signs and symptoms followed by clinically significant worsening before the assessment. Additional antimicrobial therapy required.

CONFIDENTIAL Page 53 of 88

	 Progression (worsening) of chest roentgenogram (CT scans) abnormalities or unchanged chest roentgenogram features (only for TOC visit).
	 Death because of pneumonia.
Indeterminate	• No evaluation possible: the patient was lost to follow-up, or died
	because of noninfectious-related reasons or infection other than
	pneumonia (as judged by the investigator).

10.2.3 Bacteriological study

Sputum sample for the culture (bacteriological) study for isolation of pathogens will be collected before the initiation of therapy on Day 1 of the study (at Visit 1, during screening procedures) and before the first oral dose of IMP on Day 4(8) of the study (Visit 2, switch to oral therapy), within 1-2 days (Visit 3) and within 7-9 days (Visit 4) after the last dose. This procedure will be performed only if it will be necessary and possible (according to the judgment of the investigator) to collect the sputum from patient (deep expectorated / broncho-alveolar lavage, etc.).

Blood sample collection for bacteriological study will be done before the initiation of the therapy on Day 1 (at Visit 1, screening procedures) and before dosing on Day 4(8) of the study (at Visit 2, switch to oral therapy), within 1-2 days (Visit 3) and within 7-9 days (Visit 4) after the last dose. However blood sampling at Visit 2, 3 and 4 should not be conducted if no bacterial growth has been detected by blood cultures of samples withdrawn at Visit 1.

The results of bacteriological study will be documented in eCRF.

Causative pathogens of CAP listed below will be determined in sputum/blood samples:

- S. pneumoniae
- H. influenzae
- S. aureus
- K. pneumoniae
- P. aeruginosa
- Other.

Bacteriological study will be performed in the local laboratory of investigational site. After isolation of pathogens culture from some previously defined laboratories can be sent to a central laboratory for additional investigations by a decision of the Sponsor. Detailed information about central laboratory, conditions of culture transportation are provided in appropriate Manual. The Sponsor will use these isolates to perform additional culture (bacteriological) studies, including drug sensitivity test, etc..

10.2.4 Infection relapse assessment

Within 21-23 days after the last dose (Visit 5) the investigator will ask the patient whether he/she has any signs/symptoms of community-acquired pneumonia. In some cases the investigator may invite the patient to visit the clinic for the additional examinations:

- Physical examination
- Assessment of vital signs

CONFIDENTIAL Page 54 of 88

- Haematology test
- Chest X ray (two-dimensional roentgenogram) or chest computed tomography
- Collection of a sputum sample for culture (if the patient has sputum)
- Collection of a blood sample for culture.

10.3 Assessment of Safety

10.3.1 Physical Examination

All physical examinations will be performed by the investigator or a sub-investigator at every visit (on each day) of the study with the exception of Long-term follow-up visit (Visit 5).

Physical examination will include the following assessments:

- performance status
- head
- eyes
- ears/nose/throat
- lymph nodes
- breast
- skin
- lungs
- heart
- abdomen
- musculoskeletal
- neurologic evaluations.

Data should be recorded in the medical history and eCRF. All clinically significant abnormal changes of physical examination results from the baseline results must be reported as AEs in the eCRF.

10.3.2 Vital Signs

The investigator or sub-investigator will assess vital signs at every visit (on each day) with the exception of Visit 5 (Long-term follow-up visit). On Day 1 of the study (Visit 1, screening procedures/initiation of therapy) all measurements will be done during screening procedures before treatment initiation and 2 hours±30 minutes after the infusion of second solution on Day 1 is finished; on each day of Days 2-3(7) of the study (Visit 1, continuation of i.v. therapy) the measurements will be done before dosing and 2 hours±30 minutes after the infusion of second solution is finished. On Day 4(8) of the study (Visit 2, switch to oral therapy) and on each day of Days 5(9)-7(14) of the study (Visit 2, continuation of oral therapy) the measurements will be done before dosing and 2 hours±30 minutes after the oral dose administration.

The following vital signs will be measured and recorded:

- pulse rate
- blood pressure (systolic and diastolic blood pressure)
- respiratory rate
- temperature.

CONFIDENTIAL Page 55 of 88

Blood pressure, pulse and respiratory rate will be measured after the patient has been seated for at least 5 minutes.

All clinically significant abnormal changes of vital signs from the baseline results must be reported as AEs in the eCRF.

10.3.3 Electrocardiography

Electrocardiogram (ECG) will be recorded before treatment initiation on Day 1 (Visit 1, screening procedures), before dosing on Day 4(8) of the study (Visit 2, switch to oral therapy), within 1-2 days (Visit 3) and within 7-9 days (Visit 4) after the last dose. ECG should be performed before or 30 minutes after collecting blood samples for haematology test, biochemical assay and blood sample collection for culture (if needed), and should start after the patient lies supine for at least 5 minutes. ECG parameters include heart rate, RR, PR, QRS, QT, and QTc.

Results of ECG will be registered in medical records and in the eCRF. All clinically significant abnormal changes of ECG results from the baseline results must be reported as AEs in the eCRF.

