3.3.1.4 Toxicological studies

The in vitro genotoxicity (mutagenicity) was considered to be related to its mechanism on inhibition of DNA gyrase by the drug. In mice micronucleus tests and rat unscheduled DNA synthesis tests, animals administered with nemonoxacin at a dose up to 2000 mg/kg did not produce in vivo genotoxicity. The drug had no potential to cause hemolytic effect in *in vitro* hemolysis test with rabbit erythrocytes.

In repeated dose toxicity studies renal tubular effects were observed at ≥ 20 mg/kg following 7 days of dosing, but these effects were not observed at up to 1000 mg/kg (AUC ≈ 130 h* μ g/mL) following 1 month of dosing in rats, or up to 500 \rightarrow 300 mg/kg (AUC ≈ 680 h* μ g/mL) in monkeys. This likely represents the large capacity of the kidney to adapt to the effect.

In the 1-month monkey study, watery stools were observed at a dose of 30 mg/kg (AUC = 60 h* μ g/mL), emesis, sinus bradycardia, and increased urine protein at a dose of 100 mg/kg (AUC = 230 h* μ g/mL), and QRS widening, decreased activity, ptosis, pale skin, dilated pupils, and thymic atrophy at a dose of 500 mg/kg (AUC = 690 h* μ g/mL). There was a dose-dependent prolongation of mean QTc and a reduction of the mean heart rate (prolonged R-R interval) for the high dose group (500/300 mg/kg) at 3 hours post dose on Days 5 and 26. The mean QTc was mildly prolonged in the female monkeys and the mean heart rate reduced for the mid dose group (100 mg/kg). The mean QTc and heart rate recovered by the subsequent 24-hour timepoint for both groups. These changes were attributed to the administration of TG-875649 (nemonoxacin malic acid salt, hemihydrate).

In a 28-day dog study, QTc prolongation was observed in dogs treated with second dose of 100 mg/kg at 1 hour post-dose, but this sign was not seen at 24 hour post-dose. No ECG change was noted after the last dose administration.

A battery of safety pharmacology studies was conducted to assess the effect of TG-873870 on the central nervous system (CNS), cardiovascular system, respiratory system, gastrointestinal (GI) system, and renal system. Based on the results of the studies it was demonstrated that TG-873870 had effects on the CNS, GI systems and on cardiac electrophysiology, which were

CONFIDENTIAL Page 26 of 88

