consistent with the known pharmacology of quinolones. The hERG and Purkinje findings suggest the possibility of QTc prolongation in man. Mild effects were also seen at the high dose (1000 mg/kg) in some CNS (decreased SMA) and GI (decreased gastric motility) studies.

Nemonoxacin did not elicit cutaneous phototoxicity when administered orally either once or repeatedly; did not produce systemic hypersensitive reactions during active systemic anaphylaxis test. In the bone/cartilage studies in juvenile dogs administered nemonoxacin at 10, 20, or 40 mg/kg/day for 4 weeks, the microscopic changes were noted in 2/3 males and 3/3 females of the 40 mg/kg/day dose group, the changes were graded minimal to moderate in severity and characterized by degeneration/necrosis with or without horizontal clefting and/or erosion of the articular cartilage. The nature and distribution (targeting the weight bearing area and middle zone of the proximal and distal femur) of these microscopic changes were compatible with quinolone-induced arthropathy/chondrotoxicity. No apparent changes were seen after 13 weeks recovery, suggesting a complete reversibility of the changes [28].

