3.3.2.1 Phase I clinical trials

During a randomized, double-blind, placebo-controlled, parallel-design, single ascending dose study (#2003107) carried out in the USA the safety, tolerability, and pharmacokinetics of orally administered nemonoxacin in healthy male and female volunteers were investigated. Fifty six subjects were enrolled in the study. Healthy volunteers were randomized to the nemonoxacin group and the control (placebo) group at a ratio of 3:1. Nine escalating dose cohorts, i.e. 25 mg, 50 mg, 125 mg, 250 mg, 500 mg, 1000 mg, 1500 mg, 2000 mg and 2500 mg, were planned. However, because of the AEs (pruritus and erythema), dose escalation was stopped after 1500 mg dose. Therefore, 1500 mg was defined as the maximum tolerated dose. There were no significant laboratory and ECG abnormalities and also no vital signs abnormalities. Nemonoxacin was rapidly absorbed after oral administration in the fasted state, with peak plasma concentrations attained within 1 to 2 hours post-dose. The mean terminal exponential half-life $(T_{1/2})$ was approximately 10 hours over the 25 mg to 250 mg dose range and increased to approximately 15 hours at higher doses. The mean renal clearance rate was approximately 0.09 L/h/kg; the mean oral clearance rate was approximately 0.22 L/h/kg; and the mean terminal volume of distribution was 3.8 L/kg. The mean urinary excretion was approximately 45% of the administered dose over the 25mg to 1500 mg dose range and 75% of the urinary excretion occurred within the first 24h after drug administration. In addition, the mean plasma protein binding of approximately 16% was observed over the concentration range of 141 ng/mL to 4270 ng/mL [28].

CONFIDENTIAL Page 27 of 88

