Switch to oral therapy (first oral dose)				X ¹²				
Daily oral therapy (until					XXX			

	Visit 1 ¹			Visit 2 ¹		Visit 3 ¹	Visit 4 ¹	Visit 5 ¹
Study procedures/assessments	Day 1 ²		Days 2-3(7)	Day 4(8)	Days 5(9)-7(14)	Within 1-2 days after the last dose ³	Within 7-9 days after the last dose ⁴	Within 21-23 days after the last dose
	Screening procedures	Randomization and initiation of therapy	Continuation of intravenous therapy	Switch to oral therapy	Continuation of oral therapy	End of treatment visit	Test of cure visit	Long-term follow up visit
Day 7-14 of the study)								
Compliance check		X	XXX	X	XXX			
Other								
Prior/concomitant medication and therapies	X	X	XXX	X	XXX	X	X	X

X – All procedures should be performed during one day.

XXX – All procedures should be performed every day during mentioned period of time.

- 1 All procedures of Visit 1 and Visit 2 will be performed during patient's hospital stay. All procedures of Visit 3 and Visit 4 can be performed at outpatient department. Visit 5 will be conducted as a telephone contact.
- ² The maximum duration is 24 hours after the signing of informed consent.
- ³ The Visit should be conducted at least 24 hours after the last dose of the study drug.
- ⁴ All the efforts should be made to conduct this visit (Visit 4) 7 days after the end of treatment.
- ⁵ The procedure should be done before dosing.
- ⁶ On Day 1 of Visit 1 the procedure should be done 2 hours ±30 minutes after the infusion of second solution is finished. On Days 2-3(7) of Visit 1 the procedure should be done before dosing and 2 hours ±30 minutes after the infusion of second solution is finished. At Visit 2 the procedure should be done before dosing and 2 hours ±30 minutes after capsules intake.
- ⁷ At screening, during the study selection criteria assessment, the Investigator may use laboratory test results obtained at the laboratory of the investigational site within 24 hours of study enrollment (signing of the Informed Consent Form) if he / she considers that available data are sufficient to permit a decision on whether the subject meets the selection criteria. In this case, another blood sampling procedure has to be conducted in the period from the signing of the Informed Consent Form to the start of treatment in order to evaluate all other laboratory parameters that have to be determined on Day 1 in accordance with the study protocol.

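### No scheduled post-baseline ECG falls near peak drug concentration, so a transient, peak-related QTc effect would be missed or strongly attenuated

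*Combined protocol and SAP*

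**What the plan says.** ECG results are a listed safety endpoint (section 5.2). Section 10.3.3 sets one screening ECG and three later ones. The first two are timed "before dosing on Day 4(8) of the study (Visit 2, switch to oral therapy), within 1-2 days (Visit 3", and the third is at Visit 4, 7-9 days after the last dose. Section 9.2.2 repeats the pre-dose rule for the switch day: "ECG (before dosing; before or 30 minutes after blood samples collection". A footnote to Table 9-1 sets the floor for Visit 3: "The Visit should be conducted at least 24 hours after the last dose of the study drug".

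Vital signs are handled differently. For them, Table 9-1 states: "At Visit 2 the procedure should be done before dosing and 2 hours ±30 minutes after capsules intake".

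The QTc background is in section 3.3.1.4:

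- In dogs, "QTc prolongation was observed in dogs treated with second dose of 100 mg/kg at 1 hour post-dose"; the change was not seen at 24 h.
- In monkeys, QTc was prolonged 3 h after dosing in the high-dose group, with milder prolongation in females at the middle dose. "The mean QTc and heart rate recovered by the subsequent 24-hour timepoint for both groups".
- On relevance to patients: "The hERG and Purkinje findings suggest the possibility of QTc prolongation in man".

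For oral dosing in the fasted state, section 3.3.2.1 reports absorption "with peak plasma concentrations attained within 1 to 2 hours post-dose". Section 12.7 provides change from baseline for laboratory data and vital signs. For ECG it provides only a descriptive summary by visit and arm.

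**The concern.** The protocol treats QT prolongation as a real risk. It excludes patients with QTc(F) above 450 ms (section 7.2), prohibits QT-prolonging drugs throughout (section 8.7.2), names QT prolongation among the risks of both study drugs (section 3.4), and lists levofloxacin in Appendix 3 as carrying known torsades risk. Yet every scheduled on-study ECG comes either just before a dose or a day or more after the last one.

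If an effect in patients followed the time course seen in animals, these readings would fall after it had faded. The report would then show an unremarkable ECG table in both arms, and a reader could take it as reassurance that the schedule cannot give.

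**Working it through.** The documents state no power or precision for the ECG endpoint, so there is no figure of the plan's own to reproduce.

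**Step 1. ECG times against effect times.**

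| Scheduled ECG | Time since drug |
|---|---|
| Day 4(8), pre-dose | about 22.5 h after the end of the previous 250 ml infusion (the interval that section 10.4 uses for the last pre-infusion PK sample) |
| Visit 3 | 24 h or more after the last dose |
| Visit 4 | 7-9 days after the last dose |

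The reported animal effect times are 1 h and 3 h, with recovery by 24 h. None of the three ECGs falls in that window.

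**Step 2. How far the animal exposures are from the human ones.** Monkey AUC was 230 h·µg/mL at 100 mg/kg and 690 at 500 mg/kg (section 3.3.1.4). Human AUC at 500 mg i.v., day 10, was 44.03 µg·h/mL over 22.5 h (section 3.3.2.1).

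- 230 / 44.03 = 5.2
- 690 / 44.03 = 15.7

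The sampling window of the monkey AUC is not given, so the ratios are approximate. No AUC is given for the dog finding at 100 mg/kg.

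**Step 3. Exposure left at the Day 4(8) ECG.** Concentration at the end of a dosing interval cannot exceed the mean over it, because it is the lowest point.

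- Mean = AUC / time = 44.03 / 22.5 = 1.96 µg/mL
- Mean / Cmax = 1.96 / 9.600 = 0.204

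So the pre-dose level after i.v. dosing is at most about 20% of peak. This needs no half-life assumption.

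**Step 4. Exposure left at Visits 3 and 4.** After oral dosing the protocol gives no paired Cmax and AUC, so only the half-lives in section 3.3.2.1 can be used. With a single exponential, the share of peak left is 2^(−t/half-life). At t = 22.5 h (from a peak at 1-2 h to about 24 h after the dose):

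- half-life 7-8 h: 11-14%
- half-life 10-15 h: 21-35%
- half-life 18-23 h (after 10 days of oral dosing): 42-51%

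A faster early decline would lower these shares. At 48 h the range is 1-24%; at 7 days it is below 1%.

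**Step 5. Illustration only.** Assume a 10 ms between-arm QTc difference at peak, an effect proportional to concentration, and an SD of QTc change of 15, 20 or 25 ms. None of these is in the documents. With all 171 per arm contributing, SE = SD × √(2/171) = 1.62, 2.16 or 2.70 ms.

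- Near peak (10 ms): power 1.00, 0.996, 0.96 at two-sided 0.05.
- At the i.v. trough (at most 0.204 × 10, about 2 ms): power 0.23, 0.15, 0.11.

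The planned analysis is descriptive, so read this as how visible a difference would be, not as a test that the plan promises.

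**The case against.** The strongest reply is that the worry rests on animal findings at multiples of the human exposure. The dog study showed no ECG change after the last dose. The human summaries report no significant ECG abnormality with single oral doses up to 1500 mg, no apparent interval differences over ten days up to 1000 mg, and no clinically significant change with i.v. dosing. The protocol refers to the Investigator's Brochure for detail, so peak QTc may already be characterised there. All of this stands as a limit on how likely an effect is. It does not show that this schedule could find one, because the summaries give no ECG times and concern healthy volunteers.

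Three stronger readings are tempting and are not supported:

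- **That the trial will show no QTc effect whether or not one exists.** This holds only for an effect wholly gone by 24 h. A component that persists with the longer repeat-dose half-life could still appear, reduced. An early-termination or unscheduled ECG could also fall closer to a dose by chance.
- **That the schedule contradicts the protocol's own figures.** It does not. The figures are from animals, and the text calls prolongation in man only possible. Nor does section 3.4 rank QT above the hypoglycaemia and tendon risks that it lists alongside.
- **That trough is only a few per cent of peak.** That needs an assumed half-life and distribution phase. The documents support only the bound of about 20% after i.v. dosing.

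Two objections to re-timing also carry weight. Food lowers oral Cmax by about 46% and delays median Tmax by 3 hours, and the oral dosing text sets no fasting rule, so a 2 h reading may precede the peak in fed patients. And the Day 4(8) ECG is the only scheduled ECG during treatment; moving it gives up a reading before the first oral dose.

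**Conclusion.** The point holds for a transient, peak-related QTc effect. None of the three scheduled post-baseline ECGs is near peak. The Day 4(8) reading is taken at no more than about one fifth of the i.v. peak concentration, and the other two are a day or more after treatment has ended. Such an effect would be missed or strongly attenuated, and an unremarkable ECG table would not be evidence against it.

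The i.v. bound rests on the reported 500 mg volunteer data applying to patients. The size of any effect in patients is unknown, and the documents give no QTc time course for levofloxacin, so a between-arm comparison at trough says little in either direction. This is a weakness in what the ECG endpoint can show, worth correcting because the correction is cheap. It is not evidence of a safety problem.

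**What to change.** Keep the number of ECGs the same. In Table 9-1 and sections 9.2.2 and 10.3.3, record one existing ECG at the 2 h ±30 min post-dose vital-signs slot on an oral-dosing day. There are two ways:

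- Move the Day 4(8) ECG to that slot. The switch criteria in Appendix 2 do not use an ECG, so they are unaffected.
- If the sponsor wants to keep the Day 4(8) pre-dose reading, re-time the Visit 3 ECG to that slot on an oral-dosing day. Visit 4 still gives an off-drug ECG. Section 9.2.3 then changes too, and sections 7.3 and 9.3 should say that an early-termination visit still includes an ECG, since they borrow the Visit 3 list.

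The oral slot is symmetric, because both arms take capsules at one time. After infusions it would not be, since the 250 ml infusion always precedes the 100 ml one.

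Also:

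- adjust the wording that ties the ECG to blood sampling;
- record the time from dose to meal with the ECG;
- state how patients who have not switched to oral treatment are handled;
- add to section 12.7 a summary of QTc change from the screening ECG by arm.

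The cost is the loss of one pre-dose or 24 h reading and some rewording, with one extra recorded item. The i.v. peak stays unmeasured, so the protocol should state that the ECG endpoint does not assess the QTc effect at the i.v. peak.
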